3.4. Duration of Treatment and Subject Participation

After signing the main informed consent form (ICF), screening assessments may be completed over a period of approximately 30 days.

Subjects will continue to receive NC318 until disease progression, withdrawal of consent, or intolerable toxicity (whichever comes first). After completing 12 months of treatment, if the subject is deriving benefit from NC318 and has not met any of the protocol defined conditions for withdrawal or discontinuation, the subject will be followed by the PI per standard of care. Subjects approved to continue treatment will remain on dose level assigned at the time of enrollment (unless otherwise approved for dose modification by the Sponsor). Safety reporting, documentation of disease assessments, and collection of survival status will continue per protocol.

3.5. Overall Study Duration

The study begins when the first subject signs the ICF. The end of the study will occur when all subjects have completed the last study follow-up visit or have discontinued study drug and have completed applicable follow-up assessments.

The end of the study may be declared when no more than 5 subjects remain on study drug for at least 6 months, at which point a database lock of the study may occur to allow for analysis of the study data. Any remaining subjects may continue to receive study drug and be seen by the investigator per standard of care. The investigator will be expected to monitor for and report any serious AEs (SAEs) and pregnancies, as detailed in [Sections 8.3](#) and [8.5](#). The remaining subjects will be considered on study until a discontinuation criterion is met and written notification is provided to the sponsor.

3.6. Study Termination

The investigator retains the right to terminate study participation at any time, according to the terms specified in the study contract. The investigator is to notify the institutional review board (IRB)/independent ethics committee (IEC) in writing of the study's completion or early termination, send a copy of the notification to the sponsor or sponsor's designee, and retain 1 copy for the site study regulatory file.

The sponsor may terminate the study electively, if required by regulatory decision or upon review of emerging data. If the study is terminated prematurely, then the sponsor or designee will notify the investigators, the IRBs and IECs, and regulatory bodies of the decision and reason for termination of the study.

4. SUBJECT ELIGIBILITY

Deviations from eligibility criteria are not allowed because they can potentially jeopardize the scientific integrity of the study, regulatory acceptability, and/or subject safety. Therefore, adherence to the criteria as specified in the Protocol is essential.

4.1. Subject Inclusion Criteria

A subject who meets all the following criteria may be included in the study:

- 1) Men and women aged 18 or older.
- 2) Willing and able to provide written informed consent for the study.
- 3) ECOG performance status 0 to 1.
- 4) Subjects with advanced unresectable and/or metastatic solid tumors confirmed to be TMB-H and/or MSI-H/dMMR including: Lung, Breast, HNSCC, Endometrial, Melanoma, CRC, Urothelial, Cholangiocarcinoma, and other tumors known to be TMB-H or MSI-H/dMMR.
- 5) Subjects who have disease progression after treatment with available therapies that are known to confer clinical benefit, or who are intolerant to treatment, or who refuse standard treatment.

Note: There is no limit to the number of prior treatment regimens.

6) Presence of measurable disease based on RECIST v1.1. Tumor lesions situated in a previously irradiated area, or in an area subjected to other locoregional therapy, are not considered measurable unless there has been demonstrated progression in the lesion.

7) Able to provide pretreatment tumor tissue sample (archival \leq 5 years old) or undergo tumor biopsy at Screening (must allow for adequate sample of tissue from appropriate site).

Note: Formalin-fixed, paraffin embedded (FFPE) tissue blocks are preferred to slides. Newly obtained biopsies are preferred to archived tissue.

8) Female subjects of childbearing potential (defined as female subjects who have not undergone surgical sterilization with a hysterectomy and/or bilateral oophorectomy and are not postmenopausal, defined as \geq 12 months of amenorrhea not caused by reversible conditions, diseases, or medications) and non-sterilized male subjects must agree to take appropriate precautions to avoid pregnancy or fathering children (with at least 99% certainty) from screening through 90 days after the last dose of study drug.

Note: Females subjects of childbearing potential must have negative serum pregnancy test at screening.

4.2. Subject Exclusion Criteria

A subject who meets any of the following criteria will be excluded from the study:

- 1) Inability to comprehend or unwilling to provide informed consent.
- 2) Laboratory and medical history parameters not within the Protocol-defined range.
 - a. Absolute neutrophil count $< 1.5 \times 10^9/L$.
 - b. Platelets $< 100 \times 10^9/L$.
 - c. Hemoglobin $< 9 \text{ g/dL}$ or $< 5.6 \text{ mmol/L}$.
 - d. Serum creatinine $> 1.5 \times$ institutional upper limit of normal (ULN) OR measured or calculated creatinine clearance $< 30 \text{ ml/min}$ for subjects with creatinine levels $< 1.5 \times$ institutional ULN.
 - e. Aspartate aminotransferase (AST) and alanine aminotransferase (ALT) $> 2.5 \times$ ULN with the following exceptions: Subjects with documented liver metastases: ALT, AST, and alkaline phosphatase $\leq 5 \times$ ULN. Subjects with documented bone metastases: alkaline phosphatase $\leq 5 \times$ ULN.
 - f. Total bilirubin $> 1.5 \times$ ULN. **Note:** Subjects with documented Gilbert's syndrome with elevated baseline total bilirubin $\leq 3.0 \text{ mg/dL}$ may be enrolled.
 - g. International normalized ratio (INR)/prothrombin time (PT) $> 1.5 \times$ ULN or activated partial thromboplastin time (aPTT) $> 1.5 \times$ ULN; applies only to subjects who do not receive therapeutic anticoagulation; subjects receiving therapeutic anticoagulation should be on a stable dose.

3) Transfusion of blood products (including platelets or red blood cells) or administration of colony-stimulating factors (including granulocyte colony-stimulating factor, granulocyte macrophage colony-stimulating factor, or recombinant erythropoietin) within 7 days prior to first administration of study drug.

4) Receipt of anticancer medications or investigational drugs within the following intervals before the first administration of study drug:

- a. \leq 14 days for chemotherapy, targeted small molecule therapy, or radiation therapy. Subjects must not have had radiation pneumonitis because of a treatment. A 1-week washout is permitted for palliative radiation to non-central nervous system (CNS) disease provided recovery is adequate.

Note: Bisphosphonates and denosumab are permitted medications.

- b. \leq 28 days for prior immunotherapy or persistence of active cellular therapy (e.g., chimeric antigen receptor T cell therapy; other cellular therapies must be discussed with the medical monitor to determine eligibility).
- c. \leq 28 days for a prior mAb used for anticancer therapy except for denosumab.
- d. \leq 7 days for immune-suppressive-based treatment for any reason.

Note: Use of inhaled or topical steroids or corticosteroid use for radiographic procedures is permitted.

Note: The use of corticosteroids equivalent to prednisone \leq 10mg/day is allowed.

- e. \leq 28 days or 5 half-lives (whichever is longer) before the first dose for all other investigational study drugs or devices.
- f. \leq 14 days for a COVID-19 vaccine. **Note:** For 2-dose COVID-19 vaccines, subjects must wait at least 14-days after 2nd dose administration.

5) Has not recovered to \leq Grade 1 from toxic effects of prior therapy (including prior immunotherapy) and/or complications from prior surgical intervention before starting therapy.

Note: Subjects with stable chronic conditions (\leq Grade 2) not expected to resolve (such as neuropathy and alopecia) are exceptions and may enroll.

Note: Subjects with a history of any grade immune-related ocular AE (e.g., episcleritis, scleritis, uveitis) will be excluded.

Note: Subjects with a history of a Grade 3 or higher irAE from prior immunotherapies are excluded from the Phase 1a dose-escalation portion of the study.

6) Receipt of a live vaccine within 30 days of planned start of study therapy.

Note: Examples of live vaccines include, but are not limited to, the following: measles, mumps, rubella, chicken pox/zoster, yellow fever, rabies, Bacillus Calmette-Guérin, and typhoid vaccine. Seasonal influenza vaccines for injection are generally killed virus vaccines and are allowed; however, intranasal influenza vaccines (e.g., FluMist®) are live attenuated vaccines and are not allowed.

7) Active autoimmune disease that required systemic treatment in the past (i.e., with use of disease-modifying agents, corticosteroids, or immunosuppressive drugs).

Note: Subjects with hyperthyroidism or hypothyroidism, who have not required any systemic treatment for an autoimmune disease for at least 2 years and have normal thyroid function or are stable on thyroid hormone replacement are allowed to participate in the study.

Note: Replacement and symptomatic therapies (e.g., levothyroxine, insulin, or physiologic corticosteroid replacement therapy for adrenal or pituitary insufficiency, etc.) are not considered a form of systemic immune suppressive therapy and are allowed.

8) Known active CNS metastases and/or carcinomatous meningitis.

Note: Subjects with previously treated brain metastases may participate provided they are stable (without evidence of progression by imaging for at least 28 days before the first dose of study drug and any neurologic symptoms have returned to baseline), have no evidence of new or enlarging brain metastases or CNS edema, and have not required steroids for at least 7 days before the first dose of study drug.

9) Known additional malignancy that is progressing or requires active treatment, or history of other malignancy within 2 years of study entry after treatment with curative intent.

Note: Cured basal cell or squamous cell carcinoma of the skin, superficial bladder cancer, prostate intraepithelial neoplasm, carcinoma in situ of the cervix, or other noninvasive or indolent malignancy, or cancers from which the subject has been disease free for > 1 year are not considered exclusionary.

10) Has a history of (non-infectious) pneumonitis / interstitial lung disease that required steroids or has current pneumonitis / interstitial lung disease.

11) Documented known activating or driver mutations (i.e. EGFR mutations/amplification, BRAF mutations, ALK alterations, etc.) which have not been previously treated with a standard of care targeted therapy.

12) Subjects with screening QTc interval > 470 milliseconds (corrected by Fridericia) are excluded.

13) Uncontrolled systemic fungal, bacterial, viral, or other infection despite appropriate anti-infection treatment.

14) Evidence of hepatitis B virus (HBV) or hepatitis C virus (HCV), unless the hepatitis is considered to be cured.

Note: Subjects with no prior history of hepatitis B infection who have been vaccinated against hepatitis B and who have a positive antibody against hepatitis B surface antigen test as the only evidence of prior exposure may participate in the study.

Note: If HCV/HBV antibody or antigen tests are positive, reflex testing (HCV RNA and/or HBV DNA tests) should be performed prior to assessing subject eligibility.

Note: Subjects with prior hepatitis B virus [HBV] infection must have HBV viral load [VL] < 100 IU/mL before study enrollment and must be treated according to local standards;

hepatitis C virus [HCV] infection must have, before study enrollment, no detectable VL and must be treated according to local standards.

- 15) Known history of HIV (HIV 1 or HIV 2 antibodies).
- 16) Known allergy or reaction to any component of study drug or formulation components.
- 17) Is pregnant or breastfeeding or expecting to conceive or father children within the projected duration of the study, starting with the screening visit through 90 days after the last dose of study treatment.
- 18) Any condition that would, in the investigator's judgment, interfere with full participation in the study, including administration of study drug and attending required study visits; pose a significant risk to the subject; or interfere with interpretation of study data.

5. TREATMENT

5.1. Treatment Assignment

5.1.1. Subject Numbering and Treatment Assignment

All subjects will sign an ICF and be assigned a unique 4-digit subject number within the case report form (CRF). The subject numbering process is defined in the CRF completion guidelines.

Investigative sites must complete all applicable CRFs for subjects consented to the trial, even if the subject is not treated with study drug.

Dose level and cohort assignment will occur at time of subject enrollment and as indicated by the sponsor. Dose level and cohort assignment will be maintained within the CRF per the CRF completion guidelines.

All subjects will be assigned to a cohort to receive NC318; there is no placebo.

NC318 must be administered the same day the investigational product is assigned. If there is a delay in the administration of investigational product such that it will not be administered within the specified timeframe, the sponsor must be notified *immediately*.

Randomization and Blinding

This is an open-label nonrandomized study; therefore, randomization and blinding do not apply.

5.2. Study Drug

5.2.1. Description and Administration

The study drug (NC318) is available in sterile frozen liquid or sterile lyophilized formulations for IV infusion over a minimum of 30 minutes on Day 1 of each cycle (if the infusion is interrupted for any non-clinical reason, sites must notify the medical monitor). The drug product will be provided in 10 ml vials. Each vial will have 400 mg NC318. The concentration of the NC318 frozen liquid formulation is 60mg/mL; total deliverable volume is 6.7 ml. When reconstituted with sterile water, the concentration of the NC318 lyophilized product is 100mg/mL; total deliverable volume is 4.0 mL. For preparation of the study drug for infusion, NC318-01 should be diluted with

normal saline to a concentration no less than 0.2 mg/ml. The infusion site should not be used for blood sampling.

5.2.2. Supply Packaging and Labeling

Study drug is supplied in a tamper evident patient kit box containing frozen liquid drug (400 mg, 60 mg/mL) or refrigerated lyophilized NC318 vials (400 mg). For the frozen liquid formulation, the study drug name (NC318), lot number, concentration, amount of drug in vial, volume, and storage conditions appear on the vial. For the lyophilized formulation, the study drug name (NC318), lot number, amount of drug in vial, and storage conditions appear on the vial. The Pharmacy Manual contains additional information regarding supply, packaging, and labeling of study drug.

The investigator shall take responsibility for and shall take all steps to maintain appropriate records and ensure appropriate supply, storage, handling, distribution, and usage of study drug in accordance with the Protocol and any applicable laws and regulations.

5.2.3. Storage

Study drug must be stored in a freezer (-20°C to -50°C) if liquid or a refrigerator (2°C to 8°C) if lyophilized, protected from light, in a secure, controlled-access location. Receipt and dispensing of study drug must be recorded by an authorized person at the study site. Study drug may not be used for any purpose other than that stated in the Protocol. The Pharmacy Manual contains additional information regarding storage of study drug.

5.2.4. Accountability

Detailed information such as requirements for accountability and disposal of study drug can be located within the Pharmacy Manual, which will be provided separately.

5.3. Treatment Compliance

Compliance with study drug dosing will be calculated by the sponsor based on the drug accountability and infusion records documented by the site staff and monitored by the sponsor/designee.

5.4. Treatment Interruptions and Adjustments

5.4.1. Dose Modifications

Selections and modifications to the study drug are planned for dose-escalation cohorts (after consultation with the medical monitor). Dose interruptions and modifications also may occur for individual study subjects. The identification of DLTs will define the doses used in planned cohorts (see [Section 5.4.2](#)). The occurrence of DLTs and other toxicities (related or unrelated to study drug) will guide decisions for treatment interruptions and discontinuation for individual subjects. Intrasubject dose escalation is not permitted; however, once the RP2D has been determined, ongoing subjects in Phase 1 may be permitted to dose escalate to the RP2D with medical monitor approval.

5.4.2. Dose-Limiting Toxicity and Determination of Maximum Tolerated Dose

The evaluation period for DLTs will begin on Cycle 1 Day 1 and will continue up to and including Study Day (SD) 28. All DLTs will be assessed by the investigator using National Cancer Institute Common Terminology Criteria for Adverse Events (NCI CTCAE) v5.0. A DLT will be defined as the occurrence of any toxicity in [Table 3](#), **except for** events clearly associated with the underlying disease, disease progression, a concomitant medication, or comorbidity.

Table 3: Definition of Dose-Limiting Toxicity (NCI CTCAE v5.0)

Nonhematologic toxicity
Any \geq Grade 3 nonhematologic toxicity EXCEPT the following: 
• Transient (\leq 72 hours) abnormal laboratory values without associated clinically significant signs or symptoms.• An event clearly associated with the underlying disease, disease progression, a concomitant medication, or comorbidity.• Asymptomatic changes in lipid profiles.• Asymptomatic changes in amylase and lipase.• Single or non-fasting elevations in blood glucose 
Note: Any grade ≥ 3 non-hematologic toxicity should count as DLTs except those that are clearly and incontrovertibly due to disease progression or extraneous causes.

Hematologic toxicity

• Grade 3 thrombocytopenia with clinically significant bleeding (i.e., requires hospitalization, transfusion of blood products, or other urgent medical intervention).• Grade 4 thrombocytopenia.• \geq Grade 3 febrile neutropenia (absolute neutrophil count $< 1.0 \times 10^9/L$ and fever $> 101^{\circ}\text{F}/38.3^{\circ}\text{C}$).• Grade 4 neutropenia that does not recover to \leq Grade 2 in ≤ 3 days after interrupting study drug.• Grade 4 anemia not explained by underlying disease or some other concomitant disorder.
Immune-related toxicity

• \geq Grade 2 ocular irAEs will be considered a DLT.• Grade 3 irAEs that do not improve to baseline or at least Grade 1 in < 5 days with appropriate care or with corticosteroid therapy will be considered a DLT.• Grade 4 irAEs will be considered a DLT regardless of duration.

General

• Inability to receive the planned number of doses within the 28-day DLT period due to treatment-related toxicity, regardless of grade, will be considered a DLT.• Combined elevations in serum ALT >3 times the upper limit of normal (ULN) and bilirubin >2 ULN in the absence of alkaline phosphatase (ALP) elevation (<2 ULN)• Abnormal liver function tests as indicated by the criteria above will be considered a DLT if no other reason can be found to explain the combination of increased liver markers such as viral hepatitis A, B, or C; preexisting or acute liver disease; or another drug capable of causing the observed injury.• Any death not clearly due to the underlying disease or extraneous causes.
MTD

• In Phase 1 of the study, the MTD will be defined as 1 dose level below that at which \geq one-third of subjects in a cohort have DLTs.• In Phase 2 of the study, toxicities will continue to be monitored. If the cumulative incidence of DLTs occurs in $> 33\%$ of subjects after 6 subjects have been observed for at least 28 days, then further enrollment may be interrupted, and the investigators and sponsor will meet and reassess the MTD. All AEs, regardless of the time of occurrence on study, may be considered in determining the appropriate dose, schedule, and MNTD.
MNTD

• Throughout the treatment period, if $> 33\%$ of subjects (minimum of 6 subjects) experience a \geq Grade 3 toxicity related to study drug after completing ≥ 4 cycles, then dose administration will be stopped, and the MNTD will be determined in conjunction with the investigators and sponsor based on all available safety data.

Abbreviations: ALP = alkaline phosphatase; DLT = dose-limiting toxicity; irAE = immune-related adverse events; MNTD = maximum number of tolerated doses; MTD = maximum tolerated dose; ULN = upper limit of normal.

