3.1.2.1. Phase 2 Safety Run-In to Evaluate New RP2D

The first 3 evaluable subjects will be observed for a DLT observation period of 28 days. Only one subject will be dosed on the first day of dosing (additional subjects can begin in \geq 48 hours). If there are no DLTs observed in the first 3 subjects, then Phase 2 Dose Expansion may begin at the new RP2D. If 1 of the first 3 evaluable subjects enrolled has a DLT, then the cohort will be expanded to include 3 additional evaluable subjects. If there are no DLTs in the additional 3 subjects, then Phase 2 Dose Expansion can begin at the new RP2D. If a DLT occurs in one-third or more of the expanded cohort, then enrollment will be paused and intermediate dose levels or alternative dose schedules may be considered.

Figure 5: Phase 2 Safety Run-In Design (3+3)

Abbreviation: DLT = dose-limiting toxicity

[figure not shown]

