n The initial tumor imaging will be performed within 30 days before the first dose of study drug. Scans performed as part of routine clinical management are acceptable for use as the screening scan if they are of diagnostic quality and performed within 30 days before the first dose of study drug. The same imaging technique should be used for a subject throughout the study. Local reading (investigator assessment with site radiology reading) will be used to determine eligibility and for subject management.

o On-study imaging will be performed at Week 8 and then every 8 weeks (56 days \pm 7 days) for the first 6 months and then every 12 weeks (84 days \pm 7 days) thereafter. After completing 12 months of treatment, subjects will have imaging performed per standard of care and PI discretion. Imaging should follow calendar days and should NOT be adjusted for delays in cycle starts. If imaging shows disease progression, then another imaging assessment should be performed 4 to 6 weeks later to confirm progression per mRECIST.

p For subjects who discontinue for reasons other than disease progression, radiologic evaluation should be repeated at the time of treatment discontinuation (i.e., date of discontinuation \pm 4-week window). If scan was obtained within 4 weeks prior to the date of discontinuation, then a scan at treatment discontinuation (EOT) is not mandatory.

Table 8: Schedule of Local Laboratory Assessments

Visit Day (Range)	Protocol Section	Screening ^a	Treatment	Post-Treatment
			Day 1 of All Cycles	EOT
		Day - 30 to - 1	D1^{b,c}	
Evaluation/Window			Predose	
Comprehensive Metabolic Panel (CMP) ^d – serum	7.5.5	X	X	X
Complete Blood Count (CBC) with differential ^e	7.5.5	X	X	X
Coagulation panel ^f	7.5.5	X		X
Urinalysis ^g	7.5.5	X		X
Endocrine function tests ^h	7.5.5	X	X	X
Hepatitis B and C ⁱ	7.5.5.2	X		
Serum pregnancy test ^j (childbearing females only)	7.5.5.1	X ^j		X
Urine pregnancy test ^k (childbearing females only)	7.5.5.1		X ^l	

Abbreviations; CBC = complete blood count; CMP = comprehensive metabolic panel; D = day; EOT = end-of-treatment.

a Lab tests must be performed during screening period (within 30 day window).

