b Cycle 1 Day 1 laboratory samples must be collected prior to study drug administration. Results should be reviewed by the investigator or qualified designee and found to be acceptable prior to the start of study drug treatment. **Note:** If screening labs were preformed within 7 days of Cycle 1 Day 1, results from screening can be used as indicator to begin study treatment.

c For all subsequent cycles after Cycle 1, pre-dose laboratory procedures may be performed up to 72 hours prior to study drug administration. Results should be reviewed by the investigator or qualified designee and found to be acceptable before the subsequent cycle of treatment is initiated.

d Chemistry required analytes in [Table 8](#).

e Hematology required analytes in [Table 8](#).

f Coagulation panel required analytes in [Table 8](#).

g Urinalysis required analytes in [Table 8](#). Urine dipstick – if positive, perform microscopic urinalysis.

h Endocrine function tests required analytes in [Table 8](#).

i Hepatitis testing required analytes in [Table 8](#).

j Pregnancy testing is required for females of child-bearing potential. A serum pregnancy test must be performed at screening.

k If positive, confirm results with serum pregnancy test.

l For women of child-bearing potential only, Day 1 urine pregnancy must be performed and resulted before study drug administration.

Table 9: Local Laboratory Tests: Required Analytes

Comprehensive Serum Chemistries	Complete Blood Count (w/ differential)	Urinalysis	Hepatitis Screening	Coagulation
Albumin	Complete blood count, including:	Color and appearance	Hepatitis B surface antigen	PT
Alkaline phosphatase	Hemoglobin	pH and specific gravity	Hepatitis B core antibody	aPTT
Alanine aminotransferase	Hematocrit	Bilirubin	HBV-DNA*	INR
Aspartate aminotransferase	Platelet count	Glucose	HCV antibody	
Bicarbonate	Red blood cell count	Ketones	HCV-RNA*	
Blood urea nitrogen	White blood cell count	Leukocytes		
Calcium	Mean corpuscular volume	Nitrite	*Note: If HCV/HBV antibody or antigen tests are positive, reflex testing (HCV RNA and/or HBV DNA tests) should be performed to confirm results prior to assessing subject eligibility.	
Chloride	Differential count, including:	Occult blood		
Creatinine	Basophils	Protein		
Glucose	Eosinophils	Urobilinogen		
Lactate dehydrogenase	Lymphocytes			
Phosphorus	Monocytes			
Potassium	Neutrophils			
Sodium				
Total bilirubin				

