6.2. Treatment Period

The treatment period begins on the day the subject receives the first dose of study drug (Cycle 1 Day 1). Cycle 1 Day 1 should take place within approximately 30 days after the subject has signed the ICF.

Subjects will have regularly scheduled study visits on Day 1 of every cycle. The duration of each cycle is dependent on the dosing schedule:

- **Initial Dosing: 800 mg weekly for 8 Cycles**
 - **Cycle Duration:** 7 days (+3 days after Cycle 1)
- **Subsequent Dosing (Cycle 9 onwards):** 800 mg every 2 weeks
 - **Cycle Duration:** 14 days (± 3 days)

For Phase 2 Safety Run-In Only: The first 4 cycles should be administered every 7 days during the DLT period.

Subjects will begin with the Initial Dosing Schedule on Cycle 1 (Day 1) and continue with weekly dosing for 8 Cycles. Beginning with Cycle 9, subjects will follow the Subsequent Dosing Schedule of 800 mg every 2 weeks. **Note:** Cycle 9 should occur two weeks following the last weekly dose of NC318. Subjects will remain on the Subsequent Dosing Schedule of 800 mg every two weeks until disease progression, withdraw of consent, or intolerable toxicity (whichever comes first).

Additional visits will be required on Days 2 and 3 of Cycles 1 and 5. During study visits, the subject will have clinical and laboratory assessments as outlined in [Table 7](#) and [Table 8](#). At certain study visits, subjects will have PK, PD, and biomarker samples obtained (see [Table 10](#) and

Table 11). Toxicities will be monitored continuously and will be graded using the NCI CTCAE v5.0 criteria.

During Cycle 1, subjects will be required to stay at the study site for safety observation for 4 hours post end of infusion. For all other cycles (with the exception of Cycle 5), subjects will be required to stay at study site for 1 hour post end of infusion for observation or per PI discretion if indicated.

It is recommended that the subject does not leave the site for any reason during the safety observation period. During the safety observation period, subjects will be assessed for the onset of acute AEs.

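### In the Phase 2 safety run-in no laboratory draw after the fourth weekly dose is required before the DLT window closes, so whether a silent laboratory DLT after that dose counts depends on site scheduling

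*Combined protocol and SAP*

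**What the plan says.** Section 5.4.2 defines the window: "The evaluation period for DLTs will begin on Cycle 1 Day 1 and will continue up to and including Study Day (SD) 28". Section 3.1.2.1 applies it to the run-in: "The first 3 evaluable subjects will be observed for a DLT observation period of 28 days". Expansion may open after no DLT in 3 subjects, or after 1 in 3 followed by none in 3 more.

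For dosing in the run-in, Section 6.2 and Table 7 footnote a state: "The first 4 cycles should be administered every 7 days during the DLT period". Outside that instruction, a weekly cycle lasts 7 days with an allowance of 3 extra days after Cycle 1.

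On visits, Section 6.2 says: "Subjects will have regularly scheduled study visits on Day 1 of every cycle". The only extras are these: "Additional visits will be required on Days 2 and 3 of Cycles 1 and 5". Table 8 schedules on-treatment safety laboratory tests pre-dose under the column "Day 1 of All Cycles". Table 8 footnote c and Section 7.5.4 add: "For all subsequent cycles after Cycle 1, pre-dose laboratory procedures may be performed up to 72 hours prior to study drug administration".

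**The concern.** The run-in tests four weekly 800 mg doses before an expansion of up to 85 subjects (Section 3.3.1). Earlier experience at 800 mg is 4 subjects dosed every 2 weeks (Section 1.3.3.1). Modelled exposure on the weekly schedule is nearly ten-fold that of 400 mg every 2 weeks (Section 1.2.2).

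Several Table 3 criteria are laboratory values that can be present without symptoms: combined ALT and bilirubin elevation, Grade 4 thrombocytopenia, Grade 4 anemia, prolonged Grade 4 neutropenia, and Grade 3 or higher chemistry that persists. For these, the run-in sees only what is drawn inside the window, and the schedule does not guarantee a draw there after dose 4. Two sites with identical patients could record different DLT counts because one draws blood before the visit and the other draws on the dosing day. With 3 subjects deciding the first step, one uncounted event changes the decision. The error runs in one direction only, towards opening the expansion.

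**Working it through.** **Day count.** Take Cycle 1 Day 1 as SD 1, so dose k falls on SD 1 + 7(k − 1). Doses 1 to 5 fall on SD 1, 8, 15, 22 and 29. Exactly four lie within SD 1-28, which reproduces the plan's statement that the first 4 cycles fall in the DLT period.

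**What each scheduled draw can show.**

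| Draw | Permitted days | Latest dose it follows | Inside SD 1-28? |
|---|---|---|---|
| Cycle 2, pre-dose | SD 5-8 | dose 1 | yes |
| Cycle 3, pre-dose | SD 12-15 | dose 2 | yes |
| Cycle 4, pre-dose | SD 19-22 | dose 3 | yes |
| Cycle 5, pre-dose, on time | SD 26-29 | dose 4 | SD 26, 27, 28 yes; SD 29 no |
| Cycle 5, pre-dose, visit on SD 32 | SD 29-32 | dose 4 | no |

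Each range runs from 72 hours (3 days) before the visit to the visit day. The last row applies only if the 3-day allowance covers Cycle 5. The run-in instruction fixes the first 4 cycles at 7 days and does not mention Cycle 5, so the text leaves this open.

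**What is scheduled after dose 4 inside the window.** Table 7 footnote h and Section 7.5.2.3 require vital signs at the end of infusion, and Section 6.2 provides for about 1 hour of observation for acute events. Both fall on SD 22. No laboratory draw is required between that infusion and SD 28.

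**Effect on the gate.** Let p be the true DLT rate, f the share of DLTs that go uncounted, and r = p(1 − f). Read two or more DLTs in the first 3 subjects as not passing. Then

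P(pass) = (1 − r)³ + 3r(1 − r)² × (1 − r)³.

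For p = 1/3:
- f = 0: r = 0.333; 0.296 + 0.444 × 0.296 = 0.428.
- f = 12.5%: r = 0.292; 0.355 + 0.439 × 0.355 = 0.511.
- f = 25%: r = 0.25; 0.422 + 0.422 × 0.422 = 0.600.

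For p = 0.5, the same three values of f give 0.172, 0.252 and 0.351. For lower rates, going from f = 0 to f = 25% moves the result from 0.709 to 0.814 at p = 0.2, and from 0.906 to 0.944 at p = 0.1.

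The documents give neither p nor f; both are assumed. The value f = 25% would arise if every DLT were a silent laboratory event, events were spread evenly over the four doses, and every draw after dose 4 fell outside the window.

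**The case against.** The strongest reply is that the gap is narrow and partly covered.

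- **Draw day.** A reader might infer that the first draw after dose 4 is always on SD 29. The documents do not say so: if Cycle 5 is on time, three of the four permitted days lie inside the window. This stands, and it is why the problem is one of site scheduling rather than a fixed blind spot.
- **Other observation.** A reader might also infer that nothing is observed after dose 4. That is wrong. Vital signs and acute-event observation take place on SD 22, toxicity is monitored continuously (Section 6.2), and unscheduled visits are allowed (Section 6.6). Symptomatic events remain detectable in the window. What is left is findings first seen on laboratory tests.
- **Table 3 exemptions.** Table 3 exempts symptom-free nonhematologic laboratory changes lasting up to 72 hours, asymptomatic amylase, lipase and lipid changes, and single glucose elevations. Grade 3 thrombocytopenia counts only with significant bleeding, and Grade 4 neutropenia only if recovery is slow. This shrinks the realistic f.
- **Other controls.** Passing means that expansion may begin, not that it must. A formal DMC reviews Phase 2 safety (Section 8.7). Section 5.4.2 allows adverse events at any time to inform dose and schedule. These are real controls, but none makes a late laboratory event count in the gate. The cumulative-DLT rule and the rule on toxicity after 4 or more cycles both need at least 6 subjects, whereas a clean first 3 can open the expansion.
- **Design preference.** Any fixed window follows its last dose least. That is true, but here the first informative draw straddles the closing day, and the protocol does not say which side counts.

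**Conclusion.** The point holds in limited form. No safety laboratory draw after the fourth dose is required by SD 28, and the next scheduled one may fall inside or outside the window. Whether a silent laboratory DLT after dose 4 enters the 0/3 or 1/6 decision is therefore left to the site's calendar. Any miss lowers the counted rate.

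The size cannot be derived from the documents. The rise from 43% to 51% or 60% at a true rate of 1/3 illustrates assumed losses of 12.5% and 25%. A reader might take 25% as an upper bound. It is not one, because toxicity that accumulates with weekly dosing could put a larger share after dose 4; nor is it a forecast, because the Table 3 exemptions and early draws could make the true share much smaller.

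There is also a wording mismatch to settle. The evaluability definition in Section 9.2.1, written under Phase 1, asks for a full dose and then 28 days of follow-up. That can be read as reaching SD 29, a day beyond Section 5.4.2.

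This is a cheap improvement to the run-in rule. It does not show that the run-in is invalid.

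**What to change.** Reconcile the synopsis run-in text, Sections 3.1.2.1, 5.4.2, 6.2, 7.5.4 and 9.2.1, and Table 8 with footnote c, so that for the run-in:

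1. The DLT assessment includes the first scheduled laboratory draw and visit after dose 4, that is, the Cycle 5 pre-dose assessment on whatever day it is taken. Say whether the 3-day allowance applies to that visit.
2. The gate is called only when those results have been reviewed for every gating subject, together with any repeat values needed to apply the persistence and recovery criteria in Table 3. A single draw cannot settle those criteria.
3. Sections 3.3.2 and 9.2.1 state how a subject who completes SD 28 without a draw after dose 4 is treated for evaluability and replacement.

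The change uses a draw and visit already on the schedule and alters no dose, dosing schedule or toxicity criterion. It adds about one day per gating subject (SD 28 to 29), or about four if Cycle 5 slips to SD 32, plus any time for repeat values. It also slightly raises the chance of counting a DLT.
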